12.0 DATA REPORTING/REGULATORY REQUIREMENTS

12.1 Data Collection and Storage

Study outcome data will be captured in electronic case report forms (eCRFs) using an electronic data capture (EDC) system on OHSU secure servers, which facilitates information being stored in a unified format and location. To further preserve confidentiality, PHI in the EDC system will be limited to just birth date and visit dates. The web-accessible EDC system is password protected and encrypted with role-based security, and administered by designated informatics staff within OHSU or Knight Cancer Institute. All users of the database are assigned a unique ID, username, and password and must complete training appropriate to their role before they are authorized to enter, access, and store data in the database.

Basic accrual tracking information (demographic, consent, visit information) will be captured in OHSU's electronic clinical information research system (eCRIS), hosted on OHSU secure servers and managed by OHSU's information technology group at their data center in downtown Portland, Oregon. Any additional printed documents containing participant identifiers, such as those from the medical record to confirm eligibility, will be filed in binders and kept in a locked, secure location.

Data from correlative studies will be entered into the EDC system by study personnel at OHSU. All other electronic data extracts will be stored only on OHSU computers and restricted drives, limited only to study investigators and staff with authorization to access the data.

Quality assurance will be conducted as outlined in section 12.7 under data safety and monitoring.

12.2 Privacy, Confidentiality, and Data Security

Information about study subjects will be kept confidential and managed according to the requirements of the Health Insurance Portability and Accountability Act of 1996 (HIPAA). Participants will sign an authorization that includes the following:

- What protected health information (PHI) will be collected from subjects in this study
- Who will have access to that information and why
- Who will use or disclose that information

- The rights of a research subject to revoke their authorization for use of their PHI.

In the event that a subject revokes authorization to collect or use PHI, the investigator, by regulation, retains the ability to use all information collected prior to the revocation of subject authorization.

Loss of patient confidentiality is a risk of participation. Study participant identities will be kept confidential except as required by law. Subjects' samples will be identified by code only (i.e. linked, but de-identified). Subject samples will be de-identified at the time and site of collection. Electronic case report forms, participant, and study information will be kept in a password protected database. Additionally, documents containing participant identifiers, such as those from the medical record to confirm eligibility, will be filed in binders and kept in a locked, secure location in the Office of Clinical Research at each center.

Study outcome data will be captured in electronic case report forms (eCRFs) using an electronic data capture (EDC) system stored on REDCap CLOUD secure servers, which facilitates information being stored in a unified format and location. REDCap Cloud is a web-hosted application hosted by nPhase (located in Encinitas, California), and is an approved system that has been reviewed by OHSU Security. To further preserve confidentiality, PHI in the EDC system will be limited to just birth date and dates associated with patient's medical care and life events. The web-accessible EDC system is password protected and encrypted with role-based security, and administered by designated informatics staff within OHSU or Knight Cancer Institute. All users of the database are assigned a unique ID, username, and password and must complete training appropriate to their role before they are authorized to enter, access, and store data in the database.

Each subject who signs consent will be assigned a unique coded identifier consisting of numbers. This identifier will be associated with the subject throughout the duration of their participation in the trial. The coded identifier will be used to identify subject specific samples that are received both at OHSU and other sites. Blood and tissue samples collected for the purposes of this protocol will be stored until they can be analyzed and will then be destroyed.

12.3 Protocol Review

The protocol and informed consent form for this study must be reviewed and approved in writing by the OHSU Knight Cancer Institute Clinical Research Review Committee and the appropriate Institutional Review Board prior to any subject being consented on this study at OHSU.

Other participating sites must have IRB approvals of the protocol by the IRB of record before consenting any subjects.

12.4 Informed Consent

Written informed consent will be obtained from all subjects, or the legally authorized representative of the subject, participating in this trial, as stated in the Informed Consent section of the case of Federal Regulations, Title 21, Part 50. If a subject's signature cannot be obtained, and for all subjects under the age of 18, the investigator must ensure that the informed consent is signed by the subject's legally authorized representative. Documentation of the consent process and a copy of the signed consent shall be maintained in the subject's medical record. All participating sites must have IRB approval of ICF by the IRB of records before consenting any subjects.

12.5 Changes to Protocol

Any modification of this protocol must be documented in the form of a protocol revision or amendment signed by the principal investigator and approved by the CRRC and IRB before the revision or amendment may be implemented. The only circumstance in which the amendment may be initiated without regulatory approval is for a change necessary to eliminate an apparent and immediate hazard to the subject. In that event, the investigator must notify the CRRC and IRB in writing within 10 working days after the implementation. Investigators holding the IND must notify FDA of substantive changes to the protocol.

Other participating sites must submit any proposed changes to protocol to the OHSU Coordinating Center for review and endorsement before submitting or implementing changes.

12.6 Maintenance of Records

If the investigator relocates or for any reason withdraws from the study, the study records must be transferred to an agreed upon designee, such as another institution, another investigator, or to OHSU Knight Cancer Institute Clinical Trials Office. Records must be maintained according to sponsor or FDA requirements.

Following closure of the study, the investigator will maintain all site study records in a safe and secure location. The records are maintained to allow easy and timely retrieval, when needed (e.g., audit or inspection) and, whenever feasible, to allow any subsequent review of data in conjunction with assessment of the facility, supporting systems, and staff. Upon completion of study analysis, research information is stored in Records Management off-site storage. Documents are shredded on site after 50 years of storage.

Electronic case report forms, participant, and study information will be kept in an electronic password protected database indefinitely.

12.7 OHSU IRB Reporting of Unanticipated Problems and Adverse Events

Adverse event lists, guidelines, and instructions for AE reporting can be found in Section 7.0 (Adverse Events: List and Reporting Requirements).

12.8 OHSU Knight Cancer Institute Data and Safety Monitoring Plan

In addition to complete study and pharmacy files, complete records must be maintained on each subject treated on this protocol. OHSU Knight Cancer Institute, through the auditing function of the Knight Clinical Trials Office, is responsible for ensuring that all member investigators and affiliate investigators conduct clinical research studies in compliance with local IRB standards, FDA regulations and NIH policies and in accordance with the Data and Safety Monitoring Plan policies and procedures [here](#).

Locally initiated studies will be audited by OHSU Knight CI Auditor. Newly approved studies may be audited any time after enrollment has been initiated. Each OHSU Knight approved treatment protocol will be audited on an annual basis in accordance with the Knight Data and Safety Monitoring Plan.

It is the responsibility of each participating site's principal investigator to ensure that the study is being conducted in compliance with local IRB standards, FDA regulations, and NIH policies. It is also the responsibility of each site's principal investigator to ensure that quality assurance audits at their site are conducted according to their institution's policies and procedures. The quality assurance audit process provides assurance that reported data accurately reflects the data in the primary subject record.

Study monitoring will be performed by OHSU and will include periodic assessment of the regulatory compliance, data quality, pharmacy records and study integrity. Study records will be reviewed and directly compared to source documents and the conduct of the study will be discussed with the Lead PI. Monitors may request access to all regulatory documents, source documents, CRFs, and other study documentation for on-site inspection. Direct access to these documents is guaranteed by the investigator, who must provide support at all times for these activities.

12.9 Inclusion of Women, Minorities and Children

12.9.1 Inclusion of Women and Minorities

No OHSU Knight Cancer Institute study will focus on any particular gender, racial or ethnic subset. No subject will be excluded from the study on the basis of gender, racial or ethnic origin. Male, female and minority volunteers will be recruited for this study from the general population.

CLL occurs with higher frequency in males. CLL is also more common among the Caucasians. It is less common among African Americans and much less common among the Hispanics, Asians and American Indians. We anticipate a distribution of gender in this study that is comparable to the disease incidence. However fewer than 25% of individuals in our catchment area are designated as racial or ethnic minorities, and rarely have these individuals appeared as cancer patients. Table 11 below reflects the projected accrual for the study based on the abovementioned factors.

Table 11: Population Demographics - Oregon (%)

Ethnic Category	Sex/Gender		
	Females	Males	Total
Hispanic or Latino	5.9	5.8	11.7
Not Hispanic or Latino	44.5	43.8	88.3
Ethnic Category: Total of all subjects*	50.4	49.3	100*
Racial Category			
American Indian or Alaskan Native	0.7	0.7	1.4
Asian	1.9	1.8	3.7
Black or African American	0.9	0.9	1.8
Native Hawaiian or other Pacific Islander	0.2	0.1	0.3
White	42.1	41.5	83.6
More than one race	1.9	1.9	3.8
Unknown/Other	2.7	2.6	5.3
Racial Category: Total of all subjects*	50.4	49.5	100*
TOTALS	50.4	49.6	100*

Source: Adapted from U.S. Census Bureau, 2010

*Totals may not equal 100 due to rounding

Table 12: Projected Accrual for the Present Study

Ethnic Category	Sex/Gender			
	Females	Males	Unknown	Total
Hispanic or Latino	0-1	1	0-1	1
Not Hispanic or Latino	8	12	0-1	20
Unknown	0-1	0-1	0-1	0-1
Ethnic Category: Total of all subjects*	13	16	0-1	30*
Racial Category				
American Indian or Alaskan Native	0-1	0-1	0-1	0-1
Asian	0-1	2	0-1	2
Black or African American	0-1	0-1	0-1	0-1
Native Hawaiian or other Pacific Islander	0-1	0-1	0-1	0-1
White	13	14	0-1	27
More than one race	0-1	0-1	0-1	0-1
Unknown	0-1	0-1	0-1	0-1
Racial Category: Total of all subjects*	14	16	0-1	30*

12.9.2 Inclusion of Children

This protocol does not include children for the following reason: the number of children with CLL and NHL is limited. The most common form in children is acute lymphoblastic leukemia which has a very different biology. We plan to survey only the adult forms of these diseases and do not plan to accrue children (under 18 years of age).

12.10 Publication Plan

The results of the study will be submitted as a manuscript to a peer-reviewed scientific journal in the field of oncology for publication.

12.11 ClinicalTrials.Gov Requirements

As an applicable clinical trial (ACT) under FDAAA (FDA Amendments Act of 2007, US Public Law 110-85, Section 801), this study requires mandatory registration and results reporting into a clinical trial registry. As per Knight SOP, this trial will be registered both in NIH ClinicalTrials.gov (<http://clinicaltrials.gov>) under the OHSU Knight Cancer Institute's centrally managed organizational account. It will also be registered under the NCI's Clinical Trial Reporting Program (<https://trials.nci.nih.gov>) prior to enrollment of the first subject. Once complete, primary outcome results will be posted to ClinicalTrials.gov within 12 months of the primary completion date. This process is facilitated and monitored by Knight Clinical Trial Registration Administrator ([contact]) within the Knight Clinical Trials Office with consultation and assistance from the Knight Biostatistics Shared Resource.

13. STATISTICAL CONSIDERATIONS

The Knight Cancer Institute Biostatistics Shared Resource at OHSU will provide statistical support for Protocol Version 10.0 – February 5, 2021

this trial.

13.1 Study Design

Phase I Study Design

This is an open-label, phase I/II, dose-finding study in which safety and tolerability of escalating doses SYK inhibitor entospletinib (GS-9973) in combination with obinutuzumab in patients with relapsed/refractory chronic lymphocytic leukemia/small lymphocytic lymphoma (CLL/SLL) and NHL (FL, MCL, LPL, MZL). Since best responses for both entospletinib and obinutuzumab have been documented in CLL/SLL, the Phase II portion of the study will be limited to those patients, however additional expansion cohorts may be considered at a later date.

For the dose finding part of the study, Dose escalation will proceed within each cohort according to the following scheme. Dose-limiting toxicity (DLT) is defined in the section 5.2. The starting dose of entospletinib will be 200 mg po bid daily with one dose escalation (dose level 2) and 1 dose de-escalation. Entospletinib will be administered as a single agent for 7 days prior to C1D1 to allow for assessment of biomarkers.

Table 13. Dose levels planned for dose escalation phase of the study

Dose Level	Entospletinib (Cycles 1-12)	Obinutuzumab (Cycles 1-6) IV
-1*	200 mg daily	C1D1 – 100 mg; C1D2 – 900 mg
1	200 mg BID	C1D8 & 15 – 1000 mg
2	400 mg BID	C2-6 – 1000 mg on day 1

*Dose Level -1 will be studied only if more than one patient develops a DLT in Dose Level 1

Determination of MTD

The dosage will follow the 3+3 traditional escalation rules, starts with 3 cohorts at a planned dose level. If 0 out of 3 patients experiences DLT, dose will be escalated to the next higher level at which 3 cohort will be enrolled. If 1 out of 3 patients experiences DLT, 3 more patients will be enrolled at the same dose level. Escalation will continue if 1 of 6 patients experiences a DLT. If 2 or more patients in any dose level except for the starting dose level experience DLTs, dosing will stop, and previous dose level is determined to be MTD, unless only 3 patients have been treated at that level (the tentative MTD). If 2 or more patients in the starting dose level experience DLT, dose will be de-escalated to the -1 dose levels. A tentative MTD becomes final when a total of 6 patients are treated with less than 2 DLT, or a total of 3 patients are treated with less than 1 DLT.

Phase II Study Design

The phase II study will begin after determination of MTD. The Phase 2 study of the effect of treatment is designed as a single-stage study with a primary endpoint of efficacy (response rate: ORR, CR). [The study will go back to the Phase I stage if 2 or more out of the first six subjects \(including those treated in the Phase I\) receiving the currently identified MTD experience DLT](#)

13.2 Primary and Secondary Endpoints:

13.2.1 Primary Endpoints:

The primary endpoint of the Phase I portion of the study is to determine the maximum tolerated dose (MTD) and/or a recommended Phase II dose (RP2D) of entospletinib in combination with obinutuzumab in patients with relapsed/refractory chronic lymphocytic leukemia/small lymphocytic lymphoma (CLL/SLL) and NHL (FL, MCL, LPL, MZL) as measured by the incidence of dose limiting toxicities (see Section 5.2).

The primary efficacy endpoint of the Phase 2 portion of the study is the CR, defined as the proportion of subjects who achieve CR described in the section 11.2.1

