5.1.1 Phase I (Dose Escalation)

Patients with CLL/SLL as well as all other histologic categories of NHL will be enrolled, as specified in the eligibility criteria.

Up to three dose levels will be evaluated in the Phase I portion of the study. The dose levels of entospletinib are 200 mg po twice daily (Dose Level 1), 400 mg po twice daily (Dose Level 2) and 200 mg po daily (Dose Level -1) beginning with day 1 of cycle 1 (Table 2). The starting dose of entospletinib will be 200 mg po bid on day -7 of the run-in phase, and the same dose will be administered on day 1 of cycle 1, which will occur immediately following day -1 of the run-on phase. The first dose of obinutuzumab will be administered IV on day 1. The dose of obinutuzumab will remain unchanged at each dose level, and the last dose will be administered with cycle 6. Each cycle will last for 28 days.

Each patient will be treated for at least 12 cycles, or until a qualifying event (Section 5.4 – Duration of therapy). Both drugs will be administered during cycles 1-6, and entospletinib alone will be administered during cycles 7-12.

The dose escalation phase will follow a standard 3+3 Phase I design. At a given dose level, 3 patients will be enrolled. If all 3 patients complete ***the run-in phase and the first cycle of therapy*** (28 days) without any dose-limiting toxicities (DLTs), the next cohort of 3 patients will be enrolled at Dose level 2. If 1/3 patients develops a DLT the cohort will be expanded to 6 patients. However, if either $\geq 2/3$ or $\geq 2/6$ patients in dose

level 2 have DLTs, Dose level 1 will be defined as the MTD of the combination. The MTD will be considered RP2D and enrollment onto the Phase II part of the study will begin.

Table 2. Dose levels planned for dose escalation phase of the study

Dose Level	Entospletinib (Cycles 1-12 and thereafter) PO starting on Day -7 of the run-in phase	Obinutuzumab (Cycles 1-6) IV
-1*	200 mg daily	C1D1 – 100 mg; C1D2 – 900 mg C1D18 & 15 – 1000 mg C2-6 – 1000 mg on day 1
1	200 mg BID	
2	400 mg BID	

*Dose Level -1 will be studied only if more than one patient develops a DLT in Dose Level 1

For all the Dose Levels, should more than one patient develop a DLT in the respective Dose Level; the dose of entospletinib will be reduced according to the plan shown in Table 3. Should more than one patient develop a DLT in the Dose Level "-1", the study will be stopped.

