The decisions to escalate or de-escalate the dose of entospletinib will follow the schema in Table 3.

Table 3. Decision rules regarding dose modification for Entospletinib

Dose level (entospletinib)	Number of Participants with DLT at a Given Dose Level with C1	Decision Rule
200 mg po daily (dose level -1)	0/3	Enroll Phase II part at this dose
	1/3	Enroll 3 additional subjects
	1/6	Enroll Phase II part at this dose
	> 2/6	STOP the study
200 mg po BID (START dose level 1)	0/3	Escalate dose to 400 mg BID
	1/3	Enroll 3 additional subjects
	1/6	Escalate dose to 400 mg BID
	> 2/6	De-escalate dose to 200 mg daily
400 mg po BID (dose level 2)	0/3	Enroll Phase II part at this dose
	1/3	Enroll 3 additional subjects
	1/6	Enroll Phase II part at this dose
	> 2/6	Enroll Phase II at Dose level 1.

If no significant toxicities are observed, the dose escalation part of the study is anticipated to enroll between 6 and 12 patients. Any patient discontinuing study treatment prior to completion of the first cycle for reasons other than AEs related to the study drugs will be replaced.

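### Section 13.1's MTD rules, read literally at Dose Level -1, conflict with Section 5.1.1 and Table 3 for every final DLT result there, and need reconciling

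*Combined protocol and SAP*

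**What the plan says.** Section 13.1 fixes the ladder: "The starting dose of entospletinib will be 200 mg po bid daily with one dose escalation (dose level 2) and 1 dose de-escalation". The footnote to its dose table adds: "Dose Level -1 will be studied only if more than one patient develops a DLT in Dose Level 1".

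Under the determination of the MTD, Section 13.1 then gives these rules:

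- No DLT in three: "If 0 out of 3 patients experiences DLT, dose will be escalated to the next higher level".
- One in six: "Escalation will continue if 1 of 6 patients experiences a DLT".
- Two or more at the starting level: "If 2 or more patients in the starting dose level experience DLT, dose will be de-escalated to the -1 dose levels".
- Two or more elsewhere: "If 2 or more patients in any dose level except for the starting dose level experience DLTs, dosing will stop, and previous dose level" is the MTD, except that a level with only three patients treated is a tentative MTD. A tentative MTD becomes final with fewer than two DLTs in six patients, or none in three.

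Section 5.1.1 has rules specific to Level -1. Its text begins "Should more than one patient develop a DLT in the Dose Level", names Level -1, and ends by stopping the study. It also says that escalation and de-escalation decisions follow Table 3. For 200 mg daily, Table 3 gives "Enroll Phase II part at this dose" after 0/3 and after 1/6, and stops the study at > 2/6 as printed.

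**The concern.** Section 13.1 writes a separate rule for the starting level only. Nothing in its wording takes Level -1 out of the general rules, although -1 is reached by moving down rather than up. From -1, both the next higher level and the level treated just before it are 200 mg BID, the level that had already exceeded the DLT limit.

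The MTD or recommended Phase II dose is the Phase I primary endpoint (Section 13.2.1), and Section 13.4.1 says that it is determined by the 3+3 design. If Level -1 opens, a team working from Section 13.1 and a team working from Section 5.1.1 could take different actions on the same data. The disagreement would concern whether the study continues and at which dose, so it should not be left to interpretation during the trial.

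**Working it through.** The documents give no figure for this point, so the check is to apply each text to each final result at Level -1.

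| Result at Level -1 | Section 13.1, read literally | Section 5.1.1 and Table 3 |
|---|---|---|
| 0/3 | Next higher level, which is 200 mg BID | Phase II at -1 |
| 1/6 | Escalation continues, to 200 mg BID | Phase II at -1 |
| 2 or more; more than 3 patients were treated at 200 mg BID | Dosing stops; 200 mg BID is the MTD | Study stops |
| 2 or more; only 3 patients were treated at 200 mg BID | Dosing stops; 200 mg BID is a tentative MTD that can never become final, since it already has 2 or more DLTs | Study stops |
| 2 or more; previous level read as next lower | Dosing stops; no level exists below -1, so the MTD is undefined | Study stops |

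The texts differ in every row. Three further points follow from the documents.

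1. The first two rows conflict with Section 13.1's own ladder sentence, in which the single planned escalation is to Level 2.
2. The third row conflicts with the return rule in Section 13.1 (Phase II Study Design) and under the study schema. That rule sends the study back to Phase I if two or more of the first six patients at the identified MTD have a DLT, counting Phase I patients. A 200 mg BID level with two or more DLTs in its six patients would meet that trigger at once.
3. Section 5.1.1 and Table 3 differ as printed at exactly 2/6: the text acts on more than one DLT, the table on > 2/6. This may be a lost or mistyped symbol, and it does not alter the comparison above.

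**How often the branch would be reached.** The documents give no DLT rates, so the rates here are assumptions for illustration only. For a true DLT rate p at 200 mg BID and q = 1 - p, Level -1 opens unless the result is 0/3 or 1/6:

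P(open -1) = 1 - q³ - 3pq² × q³

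- p = 0.2: 1 - 0.512 - 0.384 × 0.512 = 0.291
- p = 0.3: 1 - 0.343 - 0.441 × 0.343 = 0.506
- p = 0.4: 1 - 0.216 - 0.432 × 0.216 = 0.691

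To see how the branches divide, split P(open -1) into leaving 200 mg BID after three patients, P(2 or more of 3) = 3p²q + p³, and leaving it after expansion to six, 3pq²(1 - q³). Then multiply by the chance of each result at -1, using a lower assumed rate there. For 0.3 at Level 1 and 0.15 at -1, the split is 0.216 and 0.290, and -1 gives 0/3 or 1/6 with probability 0.814 and two or more DLTs with probability 0.186. The products are 0.506 × 0.814 = 0.412, 0.290 × 0.186 = 0.054 and 0.216 × 0.186 = 0.040.

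| Assumed rate at Level 1 / at -1 | -1 opens, then 0/3 or 1/6 | -1 opens after 6 at Level 1, then 2 or more | -1 opens after 3 at Level 1, then 2 or more |
|---|---|---|---|
| 0.3 / 0.15 | 41% | 5.4% | 4.0% |
| 0.4 / 0.2 | 49% | 9.9% | 10.3% |
| 0.5 / 0.3 | 41% | 16.6% | 25.3% |

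Under each assumed pair, the conflict most likely to be met is the one after 0/3 or 1/6.

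**The case against.** The strongest reply is that the governing text already exists. Section 5.1.1 says that dose decisions follow Table 3, Table 3 has rows for 200 mg daily, and the text adds an explicit stop. Section 13.1 is a generic account of a traditional 3+3 design. It also fails at the top of the ladder, where 0/3 at Level 2 would escalate to a level that does not exist. On this view specific rules prevail over general ones and nobody would be misled. The decision tree announced in the schema is not shown in the text available here and may state the action at -1.

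Much of this stands as context. It makes Section 5.1.1 the more natural place to look, and it argues against treating Section 13.1 as a deliberate competing design. It does not remove the conflict. Section 13.1 spells out its own rules, neither cites nor defers to Table 3, and contains no bar on returning to a level that exceeded the DLT limit. An unseen figure cannot settle the point either way.

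A reader might go further and infer that Section 13.1 names a failed dose as the MTD and would put more patients on it. The documents do not support that as a general statement. With two or more DLTs at -1, Section 13.1 itself stops dosing. The 200 mg BID level is the MTD outright only if more than three patients were treated there and the previous level means the one treated before; the return-to-Phase-I rule would then apply at once. After 0/3 or 1/6, the move back up is contradicted by the ladder sentence and by Table 3.

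**Conclusion.** The inconsistency is real and affects every final result at Dose Level -1. It lies in written rules that give a conflicting or undefined determination of the Phase I primary endpoint, not in missing detail. Its reach is limited: it matters only if Level -1 opens, and it touches no sample size, alpha or power figure. The 29, 51 and 69% chances of opening -1 rest on assumed DLT rates of 20, 30 and 40% and on independent patients in a 3+3 scheme; they are not predictions for this trial. Nor does the finding imply that Section 5.1.1 or Table 3 holds the right rule. They differ from each other as printed at 2/6, and the choice of action is a clinical one for the sponsor.

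**What to change.** The sponsor should reconcile Section 13.1, the text of Section 5.1.1 and Table 3 so that:

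- all three state one and the same action at Dose Level -1 for 0/3, 1/6 and two or more DLTs, with the wording for exactly 2/6 settled;
- the general sentences in Section 13.1 on escalating and on taking the previous level as MTD say which dose levels they cover, and what the previous level means;
- the result agrees with the single planned escalation, the return-to-Phase-I rule and the schema's decision tree.

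No view is given here on which action is right. The cost is a few sentences in Section 13.1 and, if needed, matching edits to Section 5.1.1 and Table 3, through the amendment process of Section 12.5. No patients, procedures or analyses are added.
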